- 4. Develop, implement and assess strategies to recruit, train, and integrate peer CHW health coaches within the PCMH model.

The 36-month intervention will be conducted using a staggered entry design across four, overlapping, 12-month waves to account for CHW caseload limits. This study will test a scalable model of peer health coaching to address the millions of patients at risk for DM, using low cost, culturally congruent personnel to promote prevention of DM in PCMH practice. If successful, our study team will work with VA's Central Office and NY City's Health and Hospital Corporation to translate the model for larger scale implementation.

Characteristics of the Research Population

Number of Subjects

All 12 PC teams at VA NY Harbor and all 4 PCMH teams at BH will be eligible to participate. In our VA PROVE study, 51/52 PCPs participated in the intervention, and we expect similar rates in this project. Eligible patients will be identified through the study's pre-DM registry, which will be based on the EMR and Corporate Data Warehouse (CDW) at each site. This methodology builds on our ongoing national, retrospective cohort study of predictors of DM among veterans with pre-DM back to 2008. Based on preliminary analysis of VA NYHHS data from 2010-2012, 62% of veterans enrolled in PC without DM, have had an HbA1c test in the previous two years.

In the intervention group, we anticipate contacting 2,100 randomly selected patients (1,050 at the VA* and 1,050 at BH) to ultimately enroll about 1,100 patients (550 at the VA and 550 at BH). This outreach sample reflects our assumption that 20% of patients will be unreachable and that 60% of those reached will enroll in the study. Another 1,100 patients attributed to control group providers will be randomly selected as the control group, in accordance with the waiver of HIPAA authorization. As detailed below, the control group will not participate in the CHW intervention. The total sample, including the intervention and control groups, will be about 2,200 patients. This amounts to approximately 265 patients (across intervention and control groups) per wave and per clinical site.

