Such vulnerable patient populations may be excluded from CHW outreach as instructed by primary care physicians. (i.e. patient will not receive a letter about services or CHW coaching intervention).

Methods & Procedures

Control Group

The control group will not have access to CHWs. They will experience usual care in their primary care clinics. PCPs in the control group will receive reminders from the study team to order A1C tests for their patients in their study, as this pragmatically collected data is necessary to evaluate the study's main outcome.

Intervention Group: (CHW Health Coaching Integrated into Team)

CHWs will provide the diabetes prevention intervention, described below, to a randomly selected subset of eligible patients per wave in the intervention teams at each hospital. CHWs and the researchers will provide regular updates to the primary care providers in the intervention group on these activities. As with PCPs in the control group, intervention group providers will receive reminders to order follow-up A1C tests for their patients enrolled in the study.

Choice of intervention strategies for each patient: We will have patients across the entire spectrum of motivation. Since we target the full population at risk, it will include highly motivated patients, highly resistant patients and a large group in between with varying degrees of motivation and activation. Our toolkit driven approach, which includes a wide range of strategies aligned with patient activation levels, will be based on the same framework used when [name] helped revise the VA-DOD smoking cessation guidelines from a referral-based approach to a population-based one. In the revised guidelines, the underlying principle guiding all treatment decisions – which applies equally well in this proposed study – was *all patients should be offered treatment in the most intensive setting they are willing to attend*. Similarly, all patients with pre-DM will be encouraged to use the most intensive DM prevention intervention that they are willing to attend.

CHW Reach: We anticipate that up to 40% of pre-DM subjects will participate in hospital-based programs (MOVE! at VA and Healthy Lifestyles at BH) and another 10-20% will participate in the community based Diabetes Prevention Program (e.g. at local YMCAs).

Community Health Worker (CHW) Coaches - Recruitment and Training

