CHW Recruitment: We will hire and train 6 CHWs (3@VA, 3@BH), from local patient support organizations (Veteran Service Organizations and BH volunteer office, as we have done in prior CHW studies) to implement the toolkit strategies. CHW employment opportunities announcements will be created. Requirements will include: 1) evidence of a leadership role in the patient community through social support or advocacy organizations; 2) strong communication and interpersonal skills; and 3) a high school education or GED. CHW candidates will not be required to have a background in health. Personal experience with DM will not be required.

CHW Training: We will train the CHWs in key DM concepts, motivational interviewing, brief action planning, and stages of behavior change. CHWs will participate in a 105-hour core competency training developed collaboratively developed by [name] and her team and the Community Health Worker Network of New York. CHWs will conduct mock telephone counseling calls with trained standardized patients to enhance skills, gain feedback, and develop confidence in these techniques. In addition to these training experiences, CHWs will have letter templates, motivational interviewing scripts, and protocols available for patient outreach to standardize and guide patient outreach

CHW Intervention

At each wave's outset, ~ 250 patients at each study site will be randomly selected for outreach and paired with one of five CHWs (2 at BH, 2 at VA, 1 at both clinics). Researchers will provide each intervention group PC provider their selected list of prediabetic patients. PCPs will be asked to review the list to identify anyone they think should be excluded from the intervention. Patients are matched to a CHW according to the patient's language and neighborhood of residence, as the study aims to cluster CHWs' patients to facilitate CHW travel and expertise in local resources. We mail selected patients a letter on behalf of their PCP alerting them of their DM risk status, available prevention resources, and introducing them to their assigned CHW. CHWs will then call patients to describe the program and seek verbal informed consent to enroll in the study. Patients who decline participation will be asked if they are willing to be invited again in subsequent waves of the study. CHWs will continue outreach until they have met their caseload for the wave.

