We will use a similar generalized linear mixed-effects modeling for the secondary outcomes, to explore the relationship of the intervention's effectiveness to specific patient and provider or team characteristics. We will investigate interactions between the intervention and the patients' level of activation, co-morbidities (HTN, depression, and smoking), and health care utilization. We will also test the correlation (Pearson's r) of provider self-efficacy and team collective-efficacy on patient outcomes. We will conduct secondary analyses to better understand the impacts of the individual components of this complex set of interventions. While designed to test the effectiveness of an overall strategy, we will seek to determine which of the intervention elements and dose of intervention (e.g. number of phone contacts, number of mailings, successful referral to *MOVE!*, Healthy Lifestyles, DPP or other programs) were most strongly associated with any improved outcomes. We will also conduct subgroup analyses to see which subgroups may benefit more from the intervention than the others. Such group analyses are data dredging; they should be considered as exploratory analyses and any resulting findings should be confirmed by independent studies.

Because control patients are not surveyed, follow-up survey data for a given wave will serve as the control group for the following wave's baseline survey data. For example, wave 1 follow-up data will be compared against wave 2 baseline data. The data collected in the survey are secondary outcomes.

Attrition/missing data: Although the retention of patients with specific provider panels is relatively stable at the VA and BH, there are a number of reasons for changes including moving, entering a nursing home or rehab facility, not being seen in PC for >2 years, or requiring specialty-based PC. Patients seldom switch among teams or providers within teams, limiting the potential for contamination between study groups. In our VA study of panel management (PROVE), only 7% of 9,841 hypertensive patients switched teams over 12 months of follow-up. In the event that a provider changes teams and moves from one study arm to the other, patients of theirs already enrolled in the study will remain in the study arm in which they were enrolled. In waves after a

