provider has switched teams, newly enrolled patients attributed to this provider will enter the study in their provider's current study arm. For the intervention group, CHWs will contact patients when they are due for PC visits to ensure that they complete regular screenings as one of the toolkit strategies. Loss to follow-up of patients assigned to control teams is a concern, however we will address it through data reports provided to the control teams, which will include patients due for an HbA1c screening.

To limit bias due to contamination and missing values, we will assess the baseline characteristics of patients who switch teams or are removed from the panel or have incomplete repeated outcomes, and compare them with that of the other participants. The (generalized) linear mixed-effect models discussed earlier can deal with attribution problem and other missing data automatically, under the missing-at-random assumption. This model assumes that the missing information only depends on the observed information, which allows us to utilize all the observed information. To better understand the nature of our missing data and its mechanism; we will summarize the outcome variables by discontinuation status/reason in each arm. If the trajectories of the primary outcome variables from those with incomplete data are similar to those with complete information, the data may be missing at random; otherwise, it may be missing not at random. We will then conduct sensitivity analysis to assess the impact of missing not at random data on our analysis. The sensitivity analysis will test whether our primary statistical analysis remains credible if we investigate cases where those patients with incomplete data have outcomes that are unfavorable to the intervention arm of the study (e.g. those with incomplete outcome data in the control arm are less likely to develop DM, lose weight or have improved glycemic control or that those with incomplete outcome data in the intervention group are less likely to have lost weight or improved glycemic control but more likely to have developed DM). The sensitivity analysis will be conducted via multiple imputation using sequential modeling, applying a SAS macro.

Analysis: Intervention Implementation

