All primary care staff will be given information about the proposed research during regular staff meetings, email announcements and a study flyer and then asked to participate. Staff providing verbal consent to participate will be randomized (as part of their PACT team) to either work with a CHW or serve as controls. Staff who opt-out will not be randomized, although might still work on a team that is included in the study. For example, if one primary care provider in a team declines participation, the other providers and team members consent, the team will be randomized to a study arm. If that team is randomized to an intervention arm, the

CHW would only work with the patients of the consenting providers. We anticipate that we will be able to obtain sufficient numbers of staff consenting to participate, as in our previous panel management study only one PCP out of fifty-one declined, and a majority of staff reported that the interventions and CHW support were helpful. Lastly, as CHWs will be extending services and interventions that are a part of regular, evidence-based practice on behalf of patients' primary care physician, patients will not individually consent to receiving phone calls, mailings, or any other contact with the CHW. For surveys, which are research procedures specific to this study, consenting elements will be presented at the top of the survey. Primary care teams will pre-approve all lists of patients receiving interventions as well as approving the content of the CHW's intervention. Patients will have the right to opt out of receiving outreach at any time. All mail materials will include instructions on how to stop receiving mail from the CHW.

A waiver of authorization for both recruitment/identification purposes and for study procedures has been sought. We use the electronic medical record to generate a list of eligible participants, in order to approach them to screen for eligibility. Without the requested Waiver, screening could not be practically carried out and would adversely affect the scientific rigor of the study.

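### After a provider moves from an intervention to a control team, patients already selected for CHW outreach can be drawn as controls, and no flag, move log or sensitivity analysis covers this (minor).

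*Combined protocol and SAP*

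**What the plan says.** The randomised unit is the team. Under Method of Subject Identification and Recruitment, and Consent, consenting staff "will be randomized (as part of their PACT team) to either work with a CHW or serve as controls". Number of Subjects gives the clusters: "All 12 PC teams at VA NY Harbor and all 4 PCMH teams at BH will be eligible to participate". Study Design describes a "staggered entry design across four, overlapping, 12-month waves".

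The Attrition/missing data paragraph has two rules for a provider who crosses arms. For current participants, "patients of theirs already enrolled in the study will remain in the study arm in which they were enrolled". For later waves, "newly enrolled patients attributed to this provider will enter the study in their" provider's current arm.

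Four other sections decide who can then be selected:

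- Number of Subjects: "Another 1,100 patients attributed to control group providers will be randomly selected as the control group".
- CHW Intervention: selected patients are mailed a letter about their diabetes risk that introduces their assigned CHW, and are called afterwards to seek consent. "Patients who decline participation will be asked if they are willing to be invited again in subsequent waves of the study".
- Inclusion Criteria and Exclusion Criteria: neither mentions earlier selection for outreach or an earlier refusal.
- Control Group: controls have no access to CHWs.

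The contamination check in the Attrition/missing data paragraph compares baseline characteristics of patients who switch teams or leave a panel. It does not mention providers who move.

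**The concern.** Take a provider who moves from an intervention to a control team after wave 2. Patients on that panel who enrolled keep their arm. The rest are now attributed to a control-group provider and can be drawn as wave 3 or wave 4 controls. Some of them have already had the letter and perhaps a call. Some may have agreed to be invited again, and the CHW Intervention section also provides for six-monthly re-calls to patients who are not yet ready to change. This conflicts with the statement that controls have no CHW access, and the sections must be reconciled.

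Two distortions follow, in opposite directions. Earlier exposure among controls pulls the comparison toward no effect. A pool that has lost its consenters may hold less motivated patients, which could favour the intervention. Without a record of earlier selection, the two cannot be examined afterwards.

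**Working it through.** **1. The plan's own enrolment figures.** Inputs from Statistical Power and Sample Size and Number of Subjects: caseload 72, 3.5 full-time CHWs, 4 waves, 20% unreachable, 60% of those reached enrol.

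- Enrolled: 72 × 3.5 × 4 = 1,008. Selected: 1,008 / (0.80 × 0.60) = 2,100. Both match the plan.
- Of 2,100 selected: 2,100 × 0.20 = 420 unreachable, 2,100 × 0.80 × 0.40 = 672 decline, and 1,008 enrol. That is 20%, 32% and 48%.
- Selected but not enrolled: 420 + 672 = 1,092, or 52% of those selected. This is not a share of the pool from which controls are drawn.

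**2. Share of the pool.** Inputs: about 1,100 eligible at the VA, about 8,200 at BH, and 1,050 planned contacts per site, so 1,050 / 4 = 262.5 per wave. Assumptions: half of each site's eligible patients sit in intervention teams, no patients become newly eligible, and two waves are complete (525 selected per site).

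| Intervention-team patients | VA | BH |
|---|---|---|
| Eligible at start | 550 | 4,100 |
| Enrolled, 0.48 × 525 | 252 | 252 |
| Left unenrolled | 298 | 3,848 |
| Selected earlier, not enrolled, 0.52 × 525 | 273 (92%) | 273 (7%) |
| of which declined, 0.32 × 525 | 168 (56%) | 168 (4%) |
| Never selected | 25 | 3,575 |

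**3. Loss of consenters.** In an undepleted panel, 52% would not enrol if approached. In the leftover pool the share is:

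- BH: (0.52 × 3,575 + 273) / 3,848 = 55%.
- VA: (0.52 × 25 + 273) / 298 = 96%.

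Among never-selected patients it stays at 52% in expectation, because selection for outreach was random.

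**4. Exposed controls overall.** Let s be the share of a site's controls drawn from panels that moved from intervention to control. The documents give no s, so 1% to 5% is an assumption.

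- VA: 0.92 × s = 0.9% to 4.6%.
- BH: 0.07 × s = 0.07% to 0.35%.
- With controls split evenly between sites: about 0.5% to 2.5%.

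**5. Cost in power if exposure dilutes the contrast.** The plan's 80% cannot be reproduced, since no hazard ratio or ICC is given. Solving for the effect it implies, with hazard −ln(0.85)/3 = 0.0542 per year, 12 months of follow-up, two-sided 0.05, no clustering and power = Φ(√(d/4) × |ln HR| − 1.96), gives HR about 0.54 with d about 82 events.

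If a share f of controls carries a fraction k of the log effect, the control hazard is multiplied by c = (1 − f) + f × HR^k, and the observed ratio is HR / c.

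| f | Power, k = 1 (worst case) | Power, k = 0.25 |
|---|---|---|
| 2% | 78.6% | 79.6% |
| 5% | 76.3% | 78.9% |
| 10% | 72.2% | 77.8% |

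**The case against.** The strongest reply is that the design is sound where it matters and the numbers are small. Much of that stands.

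- A reader might infer that the rule breaks the randomised comparison. It does not: a new patient takes the randomised arm of the team where the provider now works. What changes over time is which panels belong to each team.
- A reader might infer that a move from control to intervention brings in a panel that was never randomised. That panel was randomised with its team, to control.
- A reader might infer that a moved provider goes on receiving CHW updates, or that unblinded staff decide the moves. The plan says "CHWs and the researchers will provide regular updates to the primary care providers in the intervention group" but not what happens after a move, and it does not say who decides moves or why. Nothing makes moves random, but that they are non-random is an inference.
- A reader might infer that the models ignore providers. The mixed-effects models cover providers and teams. Only the sentence on the mixed-effects Cox model names teams alone.
- Controls are chosen without individual consent, so about half of any control sample would not have enrolled. At BH, two waves of depletion move this only from 52% to 55%.
- The VA's 92% is an upper bound. Eligibility is reset each wave and the registry is updated, and 1,050 contacts could not come from 550 patients without new entrants or repeat invitations. Patients counted as unreachable may not have received the letter.

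What the reply does not answer is that nothing keeps a previously selected patient out of the control draw, and nothing planned would show that it had happened.

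**Conclusion.** The point holds as a minor gap. The provider-move rule, with unrestricted sampling of controls, allows patients already selected for CHW outreach to enter as controls, contrary to the Control Group section. It concerns only new entrants in later waves on panels that moved from intervention to control.

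The size cannot be established: the only switching figure, 7%, is for patients changing teams. If 1% to 5% of controls came from such panels, about 0.5% to 2.5% of all controls would have been selected earlier, nearly all at the VA. Even if each carried the full intervention effect, the loss would be at most a few points of power. These figures rest on the pool assumptions in the working and on an effect size that the plan does not state. The net direction of bias is uncertain, because dilution and loss of consenters work against each other.

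**What to change.** 1. Flag in the study registry every patient ever selected for CHW outreach, whatever the outcome, and bar flagged patients from selection as controls. Since outreach selection was random, the never-selected patients stay roughly representative of the panel.
2. Record provider moves by arm, direction and wave, and report them.
3. Pre-specify a sensitivity analysis of time to diabetes that either excludes later-wave patients of moved providers or analyses them by the arm to which the provider's team was originally randomised. Include a provider-level term in the Cox model, since one provider's patients can span two teams.

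The flag must be set prospectively to be reliable. The cost is one registry field, one sentence on control selection and one extra analysis. The downside is fewer available controls on moved panels. At BH this is negligible. At the VA such a panel might supply very few controls (25 of 298 in the illustration), so the wave would be filled from other control providers.

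Stopping all new selection from moved providers would go further, but it conditions on an event after randomisation and draws on the small VA pool. The evidence here does not require it.

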Data from the FACETS neighborhood database of social determinants will be conjoined with study data to describe whether contextual factors pertaining to NYC neighborhoods are associated with prediabetes prevalence across neighborhoods. We will use a multilevel statistical model, with patients nested within neighborhoods, to conduct this analysis.

Process Evaluation: To ensure that the intervention was delivered completely and standardized across the sites, CHWs and clinical teams, there will be continuous monitoring of process outcomes and fidelity to the protocol during the CHW intervention. We will maintain standardized protocols for each toolkit strategy and documentation of peer coaching. The CHW Coordinator will conduct quarterly assessments of the interventions, proportion of patients reached and engaged by site and CHW, fidelity to counseling protocols, and the preferred toolkit and contact strategies.

Statistical Power and Sample Size

The primary study outcome for power calculations is the annual hazard rate of incident DM.

To determine sample size, we begin with the total accessible population of about 46,000 primary care patients served at the two sites (BH and VA). Of these we exclude patients with diagnosed DM (25% at VA and 15% at BH) and those over 75 years of age (who are ineligible for this intervention). Of these eligible subjects, we estimated that about 70% will have had the HbA1c test in the last 2 years and that about 40% of these will have had a test result in the prediabetes range.

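### The control-arm example in the missing-not-at-random sensitivity analysis, on its natural reading, favours the intervention on weight and glycaemia, against the aim stated in the same sentence

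*Combined protocol and SAP*

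**What the plan says.** The Attrition/missing data paragraphs sit under Analysis: Patient Clinical Outcomes and Health Behaviors. They say that if the outcome trajectories of patients with incomplete data differ from those of complete cases, the data may be missing not at random, and a sensitivity analysis follows. Its purpose is given as: "The sensitivity analysis will test whether our primary statistical analysis remains credible" when patients with incomplete data "have outcomes that are unfavorable to the intervention arm of the study".

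A bracketed example, opened by *e.g.*, then describes each arm:

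- Control: patients with incomplete data "in the control arm are less likely to develop DM, lose weight or have improved glycemic control".
- Intervention: patients with incomplete data "in the intervention group are less likely to have lost weight or improved glycemic control but more likely to have developed DM".

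The second half is attached to the first as an alternative: "or that those with incomplete outcome data in the intervention group are less likely to have lost weight". The method is multiple imputation by sequential modelling in a SAS macro. No shift size, range of shifts or expected missing rate is given.

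On the standing of the outcomes, Statistical Power and Sample Size states: "The primary study outcome for power calculations is the annual hazard rate of incident DM". The opening of Data Analysis and Data Monitoring lists weight loss with diabetes hazard among the primary hypotheses. Study Design lists glycaemic control as a secondary clinical outcome.

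**The concern.** A scenario unfavourable to the intervention must make missing controls look good: less diabetes, more weight loss, better glycaemia. The control half puts all three outcomes after a single *less likely to*. The intervention half uses the same construction, but marks its change of direction with *but more likely* when it reaches diabetes. The control half has no such switch, so the natural reading is that missing controls lose less weight and improve less. For those two outcomes that shift helps the intervention.

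Weight loss is named in the primary hypotheses, and this analysis is the plan's check on whether the primary results can be believed. Missing data are to be expected, because clinical outcomes come only from routine visits recorded in the EMR (Data Collection). Follow-up support also differs by arm. CHWs contact intervention patients who are due for visits. For controls, the plan itself calls loss to follow-up a concern and answers it with reports of patients due for HbA1c, which do not directly address weight. If the control shift were coded as worded, the weight and glycaemia results could be reported as robust to a scenario that was partly or wholly tilted towards the intervention.

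**Working it through.** The plan has no figure for this analysis to reproduce, so the check is first of direction, then of size under assumed values.

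**Direction, on the natural reading**

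| Outcome | Missing controls | Effect on contrast | Missing intervention patients | Effect on contrast |
|---|---|---|---|---|
| Diabetes | less likely | against intervention | more likely | against intervention |
| Weight loss | less likely | **for** intervention | less likely | against intervention |
| Glycaemic improvement | less likely | **for** intervention | less likely | against intervention |

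For diabetes the two shifts add, as intended. For weight and glycaemia they oppose each other.

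**Size for weight**

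Assumed inputs, none of them in the plan: observed benefit B = 1.5 kg (extra weight loss with the intervention); missing share 20% in each arm (m_I = m_C = 0.2); shift of 2 kg per missing patient. Let d be the shift in weight loss for missing patients, positive for more loss. The benefit after the shift is

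B' = B + m_I × d_I − m_C × d_C

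- Literal, control shift only (d_C = −2): 1.5 + 0.2 × 2 = 1.9 kg
- Literal, both shifts (d_I = −2, d_C = −2): 1.5 − 0.4 + 0.4 = 1.5 kg
- Intervention shift only (d_I = −2): 1.5 − 0.4 = 1.1 kg
- Intended, both shifts (d_I = −2, d_C = +2): 1.5 − 0.4 − 0.4 = 0.7 kg

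The literal shifts cancel exactly only when m_I × d_I = m_C × d_C.

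**Range over the missing rate, as a proportion losing weight**

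Assumed shift of 10 percentage points in the probability of losing weight among missing patients. The entries are changes in the intervention-minus-control contrast, in points; positive favours the intervention.

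| Missing, intervention / control | Literal, control only | Literal, both | Intervention only | Intended, both |
|---|---|---|---|---|
| 10% / 10% | +1 | 0 | −1 | −2 |
| 20% / 20% | +2 | 0 | −2 | −4 |
| 30% / 30% | +3 | 0 | −3 | −6 |
| 10% / 20% | +2 | +1 | −1 | −3 |
| 20% / 10% | +1 | −1 | −2 | −3 |

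With equal missingness the literal pair applies no net stress. With more missing in control, it moves the contrast towards the intervention. With more missing in the intervention arm, some stress remains, but less than intended.

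**Diabetes, for comparison**

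With an assumed 5-point shift and 10% to 20% missing in each arm, the change in control risk minus intervention risk is −(m_C × 5) − (m_I × 5), which runs from −0.5 − 0.5 = −1 point to −1 − 1 = −2 points. That is the intended direction throughout.

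**The case against.** The strongest reply is that the governing rule is stated correctly in the same sentence and the disputed words only illustrate it. A careful statistician would take the direction from the rule. The sentence also has a grammatical parse that fits the aim: the subject takes three separate predicates, so that missing controls are less likely to develop diabetes, do lose weight, or do have improved glycaemia. This stands as far as it goes, and it is why the point concerns a mis-worded example and not a wrong principle. But that parse turns a likelihood into a flat statement and breaks the parallel with the intervention half. No shift size or other rule elsewhere in the plan settles the sign.

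A reader might infer that the sensitivity analysis cannot stress-test the trial's result at all. The documents do not support that, for two reasons. Incident diabetes, the primary outcome for power, is correctly signed in both arms. And the two halves are joined by *or*, so the intervention-arm scenario can be run alone, and it is then a genuine stress test for weight and glycaemia (1.1 kg against 1.5 kg under the assumed values).

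Nor do the documents show that a programmer would necessarily code the wrong sign, since the stated aim gives the right one. They leave the specification open to two opposite signs.

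**Conclusion.** The point holds for one half of one example and for two outcomes. On its natural reading, the control-arm scenario shifts missing controls towards less weight loss and less glycaemic improvement, which favours the intervention and contradicts the aim it is meant to illustrate. It matters most for weight, which is among the primary hypotheses; glycaemic control is secondary. The diabetes analysis is untouched.

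On the assumed weight values, the literal wording leaves the benefit 0.4 kg to 1.2 kg above the 0.7 kg of the intended two-arm scenario (1.1 − 0.7 = 0.4; 1.9 − 0.7 = 1.2), depending on which shifts are applied. These sizes rest wholly on the assumed missing share, shift and benefit. The sign does not depend on them.

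**What to change.** Wrong as written: reword the control-arm half to say that controls with incomplete outcome data are less likely to develop diabetes but more likely to have lost weight or improved glycaemic control. Leave the intervention-arm half unchanged. This costs one sentence in the Attrition/missing data section and a matching sign in the imputation macro. It has no effect on sample size, data collection or the primary analysis.

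Optional, and separate from the sign correction: state a grid of shifts for each arm and report the tipping point, the shift at which the conclusion changes. This supplies the shift sizes that the plan lacks, at the cost of some extra analysis.
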